The primary efficacy endpoint of the study is the percentage of subjects with clinical cure (complete resolution of signs and symptoms) at the TOC visit. Secondary efficacy endpoints include the percentage of subjects with mycological eradication (negative culture for growth of *Candida* species) at the TOC visit, the percentage of subjects with clinical cure and mycological eradication at the TOC visit, the percentage of subjects with complete resolution of symptoms at the FU visit, and the percentage of subjects with clinical improvement (partial or complete resolution of signs and symptoms with a total composite score no greater than 1) at the TOC visit.

The following treatment outcome definitions will be used for the assessment of efficacy:

Clinical Outcome

- **Clinical cure:** Complete resolution of signs and symptoms of vulvovaginal infection without need for further antifungal treatment. Specifically, for complete resolution, any sign or symptom should be absent (score = 0) by the TOC visit.
- **Clinical failure:** No response to therapy or incomplete resolution of signs and symptoms or need for additional vulvovaginal or systemic antifungal therapy. If the subject receives or self-administers topical drug therapy for the treatment of vulvovaginal irritation/pruritus such as topical analgesic or corticosteroid after completing treatment with the study drug and before the TOC visit, the subject is considered a clinical failure.

Mycological Outcome

- **Mycological eradication:** A subject with negative culture for *Candida* species.
- **Mycological persistence:** A subject with a positive culture for *Candida* species.

Safety Evaluations:

Safety will be evaluated throughout the study, including the following parameters: AEs, treatment discontinuations, physical examination, vital signs, safety laboratory tests, and prior and concomitant medications.

AEs will be recorded and reviewed at all scheduled and unscheduled study visits from the time the Informed Consent Form is signed. An abbreviated physical examination, including general appearance and an overall examination of body systems, will be conducted at Screening and at

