13.0 Non-Study Treatments

13.1 Prior and Concomitant Medications

All medications (including prescription and over-the-counter medications, supplements, and herbal products) taken from 30 days before Baseline (Day 1) through the TOC visit (Day 8 - Day 14) will be recorded on the subject's diary and in the eCRF. Only the use of antifungal medications, vaginal (topical) medications, antibiotics for any reason or any other medications to treat an AE will be recorded after the TOC visit through the last study visit (FU). Start and stop dates of concomitant medications will be recorded in the eCRF. Prior and concomitant medications will be reviewed and recorded at all scheduled and unscheduled study visits.

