18.6 Efficacy

18.6.1 Efficacy Assessments

The primary efficacy endpoint of the study is the percentage of subjects with clinical cure (complete resolution of signs and symptoms) at the TOC visit. Secondary efficacy endpoints include the percentage of subjects with mycological eradication (negative culture for growth of *Candida* species) at the TOC visit, the percentage of subjects with clinical cure and mycological eradication at the TOC visit, the percentage of subjects with complete resolution of symptoms at the FU visit, and the percentage of subjects with clinical improvement (partial or complete resolution of signs and symptoms with a total composite score no greater than 1) at the TOC visit and the absolute change in signs and symptoms score from Baseline to TOC and FU visits.

The following treatment outcome definitions will be used for the assessment of efficacy relative to baseline:

Clinical Outcome

- Clinical cure: Complete resolution of signs and symptoms of vulvovaginal infection without need for further antifungal treatment. Specifically, for complete resolution, any sign or symptom should be absent (score = 0) by the TOC visit.
- Clinical failure: No response to therapy or incomplete resolution of signs and symptoms or need for additional vulvovaginal or systemic antifungal therapy. If the

subject receives or self-administers topical drug therapy for the treatment of vulvovaginal irritation/pruritus such as topical analgesic or corticosteroid after completing treatment with the study drug and before the TOC visit, the subject is considered a clinical failure.

Mycological Outcome

- Mycological eradication: A subject with negative culture for *Candida* species.
- Mycological persistence: A subject with a positive culture for *Candida* species.

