21.0 Appendices

Appendix A: Prohibited Medications and Medications to be Administered with Caution

Prohibited Medications

The use of any topical vaginal corticoids and topical vaginal contraceptives is prohibited during the study. No systemic or topical vaginal antifungal treatment other than the study drug is allowed during the study unless used as rescue medication after the subject has been documented as not responding to study drug. No investigational drugs other than the study drug are allowed within 30 days before Screening and for the entire duration of the study. In addition, the medications listed below are also prohibited.

Strong CYP3A4/5 inhibitors and CYP3A4/5 inducers

CYP	Strong Inhibitors ^a	Inducers ^a	
3A4/5	
 • boceprevir • clarithromycin • conivaptan • indinavir • lopinavir • mibefradil 	
 • nefazodone • nelfinavir • ritonavir • saquinavir • telaprevir • telithromycin 	
 • avasimibe • carbamazepine • phenytoin • rifampin • St. John's wort • long-lasting barbiturates

- a. The CYP3A4/5 inhibitors and CYP3A4/5 inducers listed in this table are not permitted during the 7 days prior to enrollment and during study treatment until TOC.

P-glycoprotein (P-gp) substrates

P-gp Drug Substrates ^a
digoxin, colchicine

- a. The P-gp substrates listed in this table are not permitted during the 48 hours prior to enrollment or during study treatment

Medications to be administered with Caution and Monitored as Appropriate

CYP3A4 substrates

CYP	Substrates
3A4	
In vitro, ibrexafungerp (SCY-078) was an inhibitor of CYP3A mediated metabolism of midazolam, but was only a weak inhibitor of metabolism of testosterone. The clinical significance of this inhibition is unknown; caution should be exercised when administering ibrexafungerp (SCY-078) with drugs known to be CYP3A sensitive substrates with narrow therapeutic index, such as midazolam and cyclosporine.
 
Subjects receiving sirolimus, tacrolimus, warfarin, cyclosporine or amiodarone are permitted for enrollment in the study and these medications may be administered concomitantly with ibrexafungerp (SCY-078) with close monitoring. Dosing adjustments and subsequent monitoring of sirolimus and warfarin should be undertaken in accordance with product prescribing information for the respective agents.

OATP1B3 substrates

OATP	Substrate

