8.1. Primary Endpoint

The primary efficacy endpoint is defined as the proportion of mITT subjects who have a clinical cure (complete resolution of signs and symptoms) at the test-of-cure (TOC) visit.

Clinical outcomes will be assessed at the TOC Visit (Day 11) according to the following definitions:

- Clinical cure: Complete resolution of signs and symptoms of vulvovaginal infection without need for further antifungal treatment and topical vaginal drug therapy for the treatment of vulvovaginal irritation/pruritus prior to or at the TOC visit. Specifically, for complete resolution, any sign or symptom should be absent (score = 0);
- Clinical failure: No response to therapy or incomplete resolution of signs and symptoms or use of additional vulvovaginal or systemic antifungal therapy or topical vaginal drug therapy for the treatment of vulvovaginal irritation/pruritus prior to or at the TOC visit. For the subject who early terminated before TOC visit and received additional vulvovaginal or systemic antifungal therapy or topical vaginal drug therapy for the treatment of vulvovaginal irritation/pruritus prior to or at the early termination visit, the subject is considered a clinical failure.

Signs of VVC will be defined as the presence of erythema, edema, or excoriation. Symptoms of VVC will be defined as itching, burning, or irritation.

Each vulvovaginal sign will be objectively scored based on severity as follows:

- 0 = none (complete absence of any signs or symptoms);
- 1 = mild (slight);
- 2 = moderate (definitely present);
- 3 = severe (marked, intense).

Each vulvovaginal symptom will be objectively scored based on severity as follows:

- 0 = none (I have no discomfort);
- 1 = mild (I have some discomfort, but it does not bother me much);
- 2 = moderate (I have discomfort, which is annoying, but not enough to affect what I am doing);
- 3 = severe (I have discomfort, which is annoying enough to affect what I am doing).

The composite score of the vulvovaginal signs and symptoms will be calculated according to the following rules and this scale has a total possible score of 18.

- If all items of the vulvovaginal signs and symptoms have been scored, the composite score is calculated as the sum of the individual scores of all 3 items of signs and 3 items of symptoms;
- If any sign or symptom is not done, the composite score will not be calculated and treated as a missing data except at FU visit;

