8.2.3. Symptom Outcome

The percentage of subjects with complete resolution of symptoms at the Follow-up (FU) visit will be analyzed by Candida Species of the baseline yeast and overall, using the same inferential analysis employing the same methods as for the primary analysis as noted in Section 8.1.1. The subjects with missing Follow-Up data for the symptom outcome will be imputed as symptom persistence using the NRI method described in Section 4.4.

Symptom outcomes will be assessed at the FU Visit according to the following definitions:

- Symptom Resolution: All symptoms are absent (score = 0) without need for further antifungal treatment or topical vaginal drug therapy for the treatment of vulvovaginal irritation/pruritus prior to or at FU visit;
- Symptom Persistence: No response to therapy or incomplete resolution of symptoms or use of additional vulvovaginal or systemic antifungal therapy or topical vaginal drug

therapy for the treatment of vulvovaginal irritation/pruritus prior to or at FU visit. For the subject who early terminated before the FU visit and received additional vulvovaginal or systemic antifungal therapy or topical vaginal drug therapy for the treatment of vulvovaginal irritation/pruritus prior to or at the early termination visit, the subject is considered a symptom persistence.

In addition, a sensitivity analysis will be conducted based on the mITT set where the subjects with the imputed symptom outcome using the NRI method at the FU visit will be removed from the analysis.

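### The clinical-failure rule counts treatment of vulvovaginal irritation or itching only when it is topical, so a sign-free woman whose symptoms are suppressed at TOC by a systemic drug taken for them is scored a cure

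*Protocol*

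**What the plan says.** **Failure rule.** The protocol synopsis states the condition as "If the subject receives or self-administers topical drug therapy for the treatment of vulvovaginal irritation/pruritus such as topical analgesic or corticosteroid", and section 18.6.1 repeats it. The subject is then a clinical failure if this happens after study drug is completed and before TOC. SAP 8.1 lists as failure the use of antifungal therapy "or topical vaginal drug therapy for the treatment of vulvovaginal irritation/pruritus prior to or at the TOC visit".

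**Cure.** Protocol 18.6.1 requires "Complete resolution of signs and symptoms of vulvovaginal infection without need for further antifungal treatment", with every item scored 0. SAP 8.1 adds a condition on symptomatic treatment: "without need for further antifungal treatment and topical vaginal drug therapy for the treatment of vulvovaginal irritation/pruritus". In these definitions in both documents, the word systemic is attached only to antifungal therapy.

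**Secondary endpoints.** Clinical improvement at TOC (SAP 8.2.4) carries the same topical condition. So does symptom resolution at FU (SAP 8.2.3): "All symptoms are absent (score = 0) without need for further antifungal treatment or topical vaginal drug therapy".

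**Prohibited drugs.** Protocol Appendix A states: "The use of any topical vaginal corticoids and topical vaginal contraceptives is prohibited during the study". Neither it nor section 13.2 lists oral antihistamines, oral analgesics or systemic corticosteroids.

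**Recording.** Protocol 13.1 requires recording of "All medications (including prescription and over-the-counter medications, supplements, and herbal products) taken from 30 days before Baseline (Day 1) through the TOC visit". After TOC, recording narrows to antifungals, topical vaginal products, antibiotics and drugs given for an adverse event (protocol 13.1 and 14.19; SAP 7.1).

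**The concern.** Three of the six items that must be 0 for cure are burning, itching and irritation, which the subject rates herself. A drug taken to relieve those complaints can produce a 0 that says little about the infection. The rule already treats such use as failure and names analgesics and corticosteroids as examples, but it is limited by route. Two women can have the same complaint, take a drug for the same reason and record the same zero scores. The one who used a topical product is a failure, and the one who took a tablet is a cure.

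At stake are the accuracy of the reported cure rates and a little power. Under the planning assumptions 70% of placebo subjects and 50% of active subjects are true failures, so equal masking per failure adds more false cures on placebo and narrows the difference. Replacing the SAP's topical wording with the protocol's would leave this gap open, because both are limited to topical use.

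**Working it through.** **1. Does anything else in the plan catch this case?**

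- *Incomplete resolution as failure:* no. Resolution is defined as a score of 0, and the score is 0.
- *Prohibited medications (protocol 13.2, Appendix A):* no. Systemic symptomatic drugs are not listed.
- *Per-protocol (PP) set (SAP 4.3):* not clearly. It excludes major deviations, but a drug that is not prohibited is not obviously a deviation. PP is in any case supportive to mITT.
- *Sensitivity analysis (SAP 8.1.1):* no. It removes only outcomes imputed as non-response.
- *Systemic steroid summary (SAP 7.1.1):* no. It covers the 30 days before baseline and enters no outcome.

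**2. Who can be misclassified?** A woman must have edema, erythema and excoriation or fissures all at 0. She must have used no antifungal and no topical vaginal drug for irritation or itching. She must have taken a systemic drug for vulvovaginal symptoms, and all three symptoms must be at 0 at TOC because of it. If any sign remains, she is already a failure.

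**3. The plan's own figure.** Inputs from protocol 18.1 and SAP 4.1: cure 50% against 30%, 2:1 allocation, Pearson chi-squared test, 5% type 1 error, 90% power. The test is two-sided (protocol 18.0).

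Pooled rate: (0.30 + 2 × 0.50)/3 = 0.4333.

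n(placebo) = [1.960 × √(0.4333 × 0.5667 × 1.5) + 1.2816 × √(0.30 × 0.70 + 0.50 × 0.50/2)]² / 0.20² = 93.2, rounded up to 94. With 188 on active, the total is 282, as stated.

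Power = Φ[(d − 1.960 × SE0)/SE1], where d is the difference in cure rates, SE0 = √(p̄(1 − p̄)(1/94 + 1/188)), p̄ is the pooled rate, and SE1 = √(p(1 − p)/94 + a(1 − a)/188) for placebo rate p and active rate a. At 30% and 50%, SE0 = 0.0626 and SE1 = 0.0597, so power = Φ(1.295) = 90.2%.

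**4. Effect of masking.** Let a share m of true failures be scored as cure, equal in both arms. Then p = 0.30 + 0.70m and a = 0.50 + 0.50m, so d = 0.20 × (1 − m).

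| m (assumed) | Placebo | Active | Difference | Power |
|---|---|---|---|---|
| 0% | 30.0% | 50.0% | 20.0 points | 90.2% |
| 1% | 30.7% | 50.5% | 19.8 points | 89.5% |
| 2% | 31.4% | 51.0% | 19.6 points | 88.7% |
| 5% | 33.5% | 52.5% | 19.0 points | 86.3% |

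**5. Can the rule be applied from planned data?** At TOC, yes. All medications are recorded through that visit, and the topical rule already depends on knowing why a product was used. The documents name only start and stop dates explicitly, so capture of the reason for use needs confirming. After TOC, no. A systemic drug for residual itching would be recorded only if it treated an adverse event, and protocol 16.1 generally excludes symptoms of the studied disease from adverse events unless they worsen or are more severe than expected.

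**The case against.** **The route limit may be deliberate.** Neither document gives a reason for the rule, and the limit is the same in both. A choice to count only treatment at the disease site is possible. That is fair, but it would not make a drug-suppressed symptom score more informative, and the plan does not say that this choice was made.

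**The pathway is narrow.** This stands. All three signs must be 0, and the drug must suppress all three symptoms. A reader might infer that any oral antihistamine or analgesic taken for itching yields a cure. It does not if signs or residual symptoms remain.

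**A larger loss of power is tempting but unsupported.** Adding 2 points on placebo and none on active (32% against 50%) gives 82.8% power, and 35% against 51% gives 72.5%. The arithmetic is right, but these cases assume masking shares per failure of 2.9% against 0% (0.02/0.70 and 0/0.50) and 7.1% against 2.0% (0.05/0.70 and 0.01/0.50). Nothing in the documents supports a higher share per failure on placebo.

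**The planning rates may already include masking.** The Phase 2b cure definition summarised in protocol 7.1 mentions no symptomatic treatment. Its rate was 52% (14 of 27) at the 600-mg total dose. If the planned 50% reflects that result, adding masking on top counts it twice. The documents do not say how the rate was chosen, so the table is best read as an upper illustration for each share.

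**A purpose-based rule also fails early, transient use.** A woman who takes one tablet soon after dosing and is symptom-free without treatment at TOC would become a failure, although protocol 11.4 says immediate relief is not expected. This stands as a cost. The topical rule has the same property.

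**Mycological eradication is an independent check.** This is true of eradication alone. Overall success (SAP 8.2.2) requires clinical cure and so inherits the gap.

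**Conclusion.** The gap is real in the text of both documents and affects the primary endpoint and clinical improvement at TOC. Its likely effect is small: a loss of 0.7, 1.5 or 3.9 points of power (90.2% less 89.5%, 88.7% or 86.3%) at masking shares of 1%, 2% or 5%. Those shares are assumed and taken as equal in the two arms, with the planned rates treated as the true ones and the sample-size chi-squared test used in place of the stratified primary test.

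Under equal shares the bias is toward no difference, and both cure rates are slightly overstated. A reader might infer that a positive result would be in doubt. This mechanism does not support that, because masking per failure would have to be more frequent on active to inflate the difference, and the documents give no sign of it. The change is worth making because the rule is inconsistent and cheap to repair at TOC, not because the trial's conclusion depends on it.

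**What to change.** **At TOC.** In SAP 8.1 and 8.2.4, replace the route-limited condition with one defined by purpose: *any drug, topical or systemic, taken for the treatment of vulvovaginal irritation, itching or burning prior to or at the TOC visit*. Align protocol 18.6.1 if the protocol is amended. Identify use at a blinded review before database lock, from the concomitant-medication record through TOC, after confirming that the eCRF captures the reason for use. The same drugs taken for other reasons do not count. If the primary definition is to stay as it is, at minimum prespecify this rule as an mITT sensitivity analysis of clinical cure.

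**At FU.** For SAP 8.2.3, either add systemic drugs taken for vulvovaginal symptoms to the categories recorded after TOC, or leave the definition unchanged and state that such use is not captured.

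**Cost.** An SAP wording change and a small blinded review. No new data are needed at TOC if the reason for use is already captured; the first FU option needs added collection. Cure rates would be slightly lower in both arms, and some women with early, transient systemic use would count as failures.

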6.0 Schematic of Study Design

[figure not shown]

Figure 1 Schematic of Study Design

7.0 Background Information and Scientific Rationale

7.1 Background Information

Vulvovaginal Candidiasis

Vulvovaginal candidiasis (VVC) is a common fungal infection caused by *Candida* spp. and is a significant morbidity condition in women from all social classes.

Information on the incidence of VVC is incomplete, since the disease is not a reportable entity and data collection is hampered by inaccuracies of diagnosis and the use of non-representative study populations.¹ VVC affects 70%–75% of women at least once during their lives, most frequently young women of childbearing age. Approximately 40%–50% of women will experience a recurrence² and 5% to 8% of adult women have a recurrent vulvovaginal candidiasis.³

Current treatments for VVC include topical antifungals and the use of prescription oral antifungals such as single doses of fluconazole. In two vaginal candidiasis studies conducted with fluconazole, the therapeutic cure rate, defined as the resolution of signs and symptoms of vaginal candidiasis along with negative KOH examination and negative culture for *Candida*, was achieved by 55% of subjects receiving single doses of fluconazole 150 mg. The therapeutic cure rate is reduced to 40% in subjects with a history of recurrent vaginitis^{4,5}. Although a single dose of fluconazole is able to provide an acceptable therapeutic outcome for more than half of the treated individuals, the emergence of fluconazole resistance among *C. albicans* isolates and the frequency of cases caused by *C. glabrata*, a strain naturally less susceptible to fluconazole, signals the need for new therapeutic approaches.

Additionally, recurrence of VVC after fluconazole therapy is not uncommon and these exacerbations often involve the same microorganism identified in the initial episode, suggesting that a small number of *C. albicans* remain as a reservoir in the vagina after completion ofazole therapy, becoming the source of subsequent exacerbations. This may be explained by the fact that azoles are fungistatic, which means that they slow the growth of, but do not kill, the fungus and azoles are not active against certain species of *Candida* that cause VVC.

New curative approaches are needed, particularly involving agents with fungicidal activity (i.e., that are able to kill the fungus) and activity against fluconazole-resistant strains, so that the causative yeasts can be eradicated. A new therapeutic approach with these characteristics would be expected to result in improved short-term and potentially long-term outcomes for this condition.

This study aims to provide evidence of the efficacy and evaluate the safety of oral SCY-078 as a new class of antifungal agent with fungicidal activity against *Candida* spp. in the treatment of patients with VVC.

The glucan synthesis inhibitor ibrexafungerp (formerly known as SCY-078)

Ibrexafungerp (formerly known as SCY-078) is a member of a new class of antifungal agents and is an orally active, semi-synthetic, triterpenoid derivative of the natural product enfumafungin. Ibrexafungerp (SCY-078) is a structurally distinct class of glucan synthesis inhibitor (GSI) that inhibits the synthesis of the fungal cell wall polymer β -(1,3)-D-glucan. Time-kill studies have

demonstrated that ibrexafungerp (SCY-078) has *in vitro* fungicidal activity against *Candida* spp. isolates similar to that observed with the echinocandins.

Ibrexafungerp (SCY-078) is being developed as the first oral and intravenous (IV) GSI for the treatment and prevention of fungal infections caused by *Candida* and *Aspergillus* species with the potential to provide the therapeutic advantages of both an IV and oral formulation.

Antifungal activity

The spectrum and potency of activity of ibrexafungerp (SCY-078) has been evaluated by numerous independent laboratories against an extensive panel of clinically relevant yeast and mold isolates using the Clinical and Laboratory Standards Institute (M27-A3 guidelines)⁶ and European Committee on Antimicrobial Susceptibility Testing methods. Overall, the epidemiological studies have demonstrated that ibrexafungerp (SCY-078) has potent, broad-spectrum activity against the majority of the clinical isolates tested. These studies have laid the foundation in support of the use of ibrexafungerp SCY-078 for the treatment of invasive fungal infections.

Activity against *Candida* spp.

Ibrexafungerp (SCY-078) has been evaluated against >2000 *Candida* isolates, including all clinically relevant species with more than 300 *C. albicans*, more than 300 *C. glabrata* and more than 100 *C. auris* isolates tested. These *in vitro* studies have demonstrated the broad spectrum of anti-*Candida* activity of SCY-078. Additionally, ibrexafungerp (SCY-078) demonstrated *in vitro* activity against pre-formed biofilms, which is a relevant feature when addressing catheter-related *Candida* infections and, potentially, VVC. Studies conducted with azole- and echinocandin-resistant strains have shown that ibrexafungerp (SCY-078) retains activity (i.e., no significant change in minimum inhibitory concentration [MIC] compared to wild type) against >90% of azole-resistant strains and >70% of *Candida* strains with *FKS* mutations commonly associated with echinocandin resistance. Interestingly, although ibrexafungerp (SCY-078) and the echinocandins share a similar mechanism of action (β -[1,3]-D-glucan synthesis inhibition), their clearly different molecular structure provides them with some differentiating characteristics in terms of microbiological activity.

Ibrexafungerp (SCY-078) was evaluated *in vitro* against clinical isolates of echinocandin-resistant strains of *Candida* spp. containing mutations in the *FKS* gene. Overall, ibrexafungerp (SCY-078) was active against the majority of the echinocandin-resistant strains tested. Significantly, ibrexafungerp (SCY-078) was active against approximately 70% of the isolates containing the most commonly reported *FKS* mutation associated with echinocandin resistance in *C. glabrata* (S663P in *FKS2* and S645P in *FKSI*). Selection of ibrexafungerp (SCY-078) resistance *in vitro* occurs at a low frequency. A deletion at position F659 in *FKS2* of *C. glabrata* was the predominant mutation observed in these studies; notably, ibrexafungerp (SCY-078) did not select for mutations at positions S663 or S645. These results suggest that ibrexafungerp (SCY-078) inhibits glucan synthase in a manner different from that of echinocandins.

The *in vitro* studies also included several multidrug-resistant isolates. Consistent with the data described above, ibrexafungerp (SCY-078) was active against >70% of these isolates. Ibrexafungerp (SCY-078) has also demonstrated a potent activity against life-threatening and multi-drug-resistant *C. auris* strains over 100 different *C. auris* isolates, at concentrations indicative of potential clinically relevant effect. *C. auris* has been recently highlighted as a clinical alert by the Centers for Disease Control and Prevention (CDC) because of the global emergence of this fungal infection with limited therapeutic options and high mortality.

Activity against *Aspergillus* spp.

The *in vitro* activity of ibrexafungerp (SCY-078) has been evaluated against >450 clinical *Aspergillus* isolates, including most clinically relevant species and azole-resistant strains. The results demonstrated potent activity of ibrexafungerp (SCY-078) against all of the strains tested.

Murine models of invasive fungal infections

The antifungal efficacy of ibrexafungerp (SCY-078) has been evaluated in several murine models of disseminated candidiasis and aspergillosis. In a disseminated *C. albicans* model, ibrexafungerp (SCY-078) was more active than fluconazole at all doses. Murine models of SCY-078 in disseminated candidiasis caused by *C. glabrata* and *C. tropicalis* indicated activity across multiple *Candida* species. The ibrexafungerp (SCY-078) area under the concentration-time curve (AUC) in plasma necessary to achieve target efficacy in these models was estimated to be 15.4 ± 2.2 $\mu\text{M}\cdot\text{hr}$.

Nonclinical experience

Toxicology studies in rats and dogs have been conducted with ibrexafungerp (SCY-078) following oral administration for up to 90 days. Reproductive and developmental toxicity studies have also been completed. The results from the non-clinical safety program provide adequate safety support for the doses and treatment duration intended in this study.

The *in vitro* studies indicated that ibrexafungerp (SCY-078) metabolism was predominantly oxidative, with cytochrome P450 (CYP) 3A being the primary enzyme involved in its oxidative metabolism. Strong inhibitors of CYP3A would be expected to increase plasma levels of ibrexafungerp (SCY-078); therefore, the concurrent administration of ibrexafungerp (SCY-078) with such inhibitors is prohibited.

Clinical experience

To date, over 500 subjects and patients have received either oral or IV formulations of ibrexafungerp (SCY-078) in Phase 1 and Phase 2 studies.

Ibrexafungerp (SCY-078) was generally well tolerated following single oral doses of up to 1600 mg and multiple oral doses of up to 800 mg/day for 28 consecutive days in Phase 1 studies. Reported adverse events (AEs) after oral administration have been generally transient and

primarily mild to moderate in intensity. The most frequently reported AEs have been mild gastrointestinal events (nausea, vomiting, diarrhea and abdominal pain).

A Phase 2 study of oral ibrexafungerp (SCY-078) as step-down therapy from IV echinocandin in patients with invasive candidiasis has been completed. Following three to ten days of IV echinocandin therapy, 21 patients received either ibrexafungerp (SCY-078) or fluconazole. Ibrexafungerp (SCY-078) was well tolerated, with an AE profile typical of this population and comparable to the Standard of Care (SOC). The results from this study also indicated that the higher dose of ibrexafungerp (SCY-078) tested (750 mg once daily [QD]) is predicted to achieve the target exposure at steady state in the majority of patients.

A Phase 2 proof-of-concept study (SCY-078-203) of oral ibrexafungerp (SCY-078) in patients with acute vulvovaginal candidiasis (AVVC) has also been completed. In this multicenter, randomized, active-controlled, evaluator-blinded study of oral ibrexafungerp (SCY-078) compared to oral fluconazole in adult female patients with AVVC, 96 patients with an acute, moderate to severe, symptomatic episode of vulvovaginal candidiasis were randomized in a 1:1:1 ratio to receive either oral ibrexafungerp (SCY-078) 750 mg with a 1250 mg loading dose for three days, oral ibrexafungerp (SCY-078) 750 mg with a 1250 mg loading dose for five days or a single dose of oral fluconazole. Ibrexafungerp (SCY-078) was well tolerated, with the most common AEs being mild gastrointestinal events. The high clinical cure rates observed in this study are supportive of the clinically relevant antifungal activity of SCY-078 in this form of *Candida* infection.

A Phase 2, Multicenter, Randomized, Double-Blind, Double-Dummy, Active-Controlled, Dose-Finding Study to Compare the Safety and Efficacy of Oral SCY-078 (ibrexafungerp) vs. Oral Fluconazole in Subjects with Acute Vulvovaginal Candidiasis (DOVE)

The primary objective of the study was dose selection for our Phase 3 pivotal program in VVC. This Phase 2b study was a randomized, multi-center, double-blind, active-controlled, dose-finding study designed to evaluate the safety, efficacy, tolerability and pharmacokinetics of five dose regimens of oral ibrexafungerp (SCY-078) in patients with moderate-to-severe acute VVC (defined as signs and symptoms score of 7 or greater), with oral fluconazole (FLU) as a reference arm. The study enrolled a total of 186 patients and 153 patients were included in the culture-confirmed, modified, intent-to-treat population. The study was not intended, nor powered, to achieve statistically significant differences in any of the evaluated endpoints. The total doses tested ranged from 600 mg to 1800 mg and the durations explored were 1 or 3 days. The maximum duration of treatment of 3 days was based on our previous Phase 2a study, SCY-078-203, in which we showed that 3 days of treatment performed similarly to 5 days, so in the DOVE study we explored 3 days and a shorter treatment duration.

The primary efficacy endpoint was clinical cure, defined as complete resolution of all signs and symptoms at the Day 10 Test of Cure (TOC) visit without the need of additional antifungal therapy. Secondary endpoints included mycological eradication and composite endpoint including both clinical cure and mycological eradication. In this Phase 2 study, response was also evaluated as

the percentage of subjects achieving a noticeable improvement in their signs and symptoms by achieving a composite sign and symptoms score of 0 or 1, absolute change in signs and symptoms from baseline and need for rescue antifungal therapy.

All doses tested achieved meaningful clinical cure and mycological eradication rates and the dose that was considered to provide the best combination of attributes for this indication is the ibrexafungerp (SCY-078) 600-mg dose administered as 300 mg BID for 2 doses.

At Day 10, the TOC visit, the 600-mg dose showed clinical and mycological response rates in-line with the reference fluconazole arm. Specifically, the clinical cure was reported in 14 of 27 of patients (52%) in the 600-mg dose and in 14 of 24 of patients (58%) in the fluconazole arm. The percentage of patients showing 0 or 1 signs and symptoms score was also comparable, with 70% and 71% of patients reporting this improvement in the ibrexafungerp (SCY-078) 600-mg dose and fluconazole arms, respectively. The mycological eradication at this timepoint was 63% for both groups.

At Day 25, the follow-up (FU) visit, the ibrexafungerp (SCY-078) 600-mg dose showed a trend towards improved clinical and mycological outcomes when compared to the fluconazole arm. If patients had persistence or recurrence of signs and symptoms of VVC, rescue antifungal medication could be prescribed. Seven (7) patients treated with fluconazole received rescue antifungal medication, whereas one patient treated with ibrexafungerp (SCY-078) 600 mg received rescue antifungal medication. The rate of patients with zero signs and symptoms at the FU visit was 70% for the ibrexafungerp (SCY-078) 600-mg dose versus 50% for the fluconazole arm. A similar difference was observed with the "0 or 1 signs and symptoms score" analysis, with 82% of patients achieving this improvement with the ibrexafungerp (SCY-078) 600-mg dose versus 58% with fluconazole. The mycological eradication at this timepoint was also numerically higher in the 600-mg dose (48%) when compared to the fluconazole arm (38%).

Oral ibrexafungerp (SCY-078) 600-mg dose was generally well tolerated, with self-limiting (generally one-day duration), mild to moderate gastrointestinal adverse events (AEs) being the most commonly reported. Nausea was reported in three patients (10%) in the ibrexafungerp (SCY-078) 600-mg dose arm compared to two patients (6%) in the FLU arm. Diarrhea and loose stool was reported in five patients (17%) in the ibrexafungerp (SCY-078) 600-mg dose arm compared to one patient in the FLU arm (3%). Abdominal pain was reported in one patient (3%) in the ibrexafungerp (SCY-078) 600-mg dose arm compared to 5 patients (16%) in the FLU arm. No vomiting, severe AEs or discontinuations due to AEs were reported in the ibrexafungerp (SCY-078) 600-mg dose arm.

Several drug-drug interaction studies have been conducted. Ketoconazole (a strong inhibitor of CYP3A) induces a significant (5-fold) increase in ibrexafungerp (SCY-078) exposure, while diltiazem (a moderate inhibitor of CYP3A) induces a mild to moderate (<3-fold) increase in ibrexafungerp (SCY-078) exposure. Ibrexafungerp (SCY-078) did not have a clinically

meaningful effect on rosiglitazone (a CYP2C8 substrate) exposure, had only a mild effect (less than a 0.5-fold increase) on the AUC of tacrolimus (a CYP3A and P-glycoprotein [P-gp] substrate) and had no effect on the maximum concentration (C_{max}) of tacrolimus.

Ibrexafungerp (SCY-078) has the potential to be an important addition to the antifungal treatment arsenal by providing potent activity against the full spectrum of *Candida* species, including difficult-to-treat organisms, and by affording the added flexibility of both oral and IV formulations. SCY-078 through the remainder of this protocol will be referred to as ibrexafungerp from this point forward.

For additional information on ibrexafungerp, please refer to the Investigator's Brochure (IB).

